## 10 RANDOMIZATION AND BLINDING

Not applicable – single arm study.

## 11 ASSIGNMENT TO STUDY

Screening numbers will be assigned by the Principal Investigator/designee at each study site as soon as the subject has signed the informed consent. Subjects who are screened and who do not meet all entry criteria are screen failures and will be entered into a screening log; data collected on screening failures will be entered in the clinical database. Once assigned, numbers for any screening failures subjects will not be re-used.

## 12 STUDY DRUG

### 12.1 Investigational Treatment

Subjects who meet the inclusion criteria and who do not meet the exclusion criteria will be treated with investigational product P1101 (ropginterferon alfa-2b). It will be administered subcutaneously every 2 weeks at the starting dose of 100 µg (Week 0). The dose will be elevated biweekly by 50 µg until 500 µg, or until response (as defined by primary endpoint) will be achieved. The dose then will remain fixed for the study duration. Dose adjustment to prior dose will be allowed if triggered by safety or tolerability. For transition phase from previous HU treatment to P1101 (for all patients on active HU), the rules as specified in the Appendix 7 will apply.

[figure not shown]
Due to the lack of experience of administration of the study drug over 300 µg in Japanese subjects, Sponsor introduce careful observation of all the subject after the administrations over 300 µg to ensure subjects safety and to respond quickly and appropriately in emergency situations. More specifically, all the subjects will be hospitalized for the first 2 days (incl. the date of administration) when they receive the study drug over 300 µg (350, 400, 450 and 500 µg). Two days after the administration, the subjects can be discharged if there is no evidence of clinically significant adverse reactions based on the assessment by the institutional Principal Investigators at each site. All safety data up to Day 15 (from previous dose to next dose) will be collected and reviewed by Principal Investigators at each site, to determine if any of the criteria for stopping dose escalation has been met. Increase to the next higher planned dose level will only occur if the previous dose level was deemed to be safe and well-tolerated following review by Principal Investigator at each site. For the safety confirmation after administration of 500 µg, the time to dose increase to 500 µg should not exceed 32 weeks. In addition, as with the administration of 350 µg, 400 µg, and 450 µg, the Principal Investigators and sub-investigators at each medical institution assess that no drug-related adverse events requiring dose reduction/interruption/discontinuation occur within 2 weeks after dose increase (by Day 15 after the next visit) according to the protocol criteria. If the safety profile of the 500 µg dosing level for the 5 subjects in the first 6 evaluable subjects is confirmed by Coordinating Principal Investigator, Principal Investigators at each site and Sponsor's Medical Monitor, the observation based on the hospitalization for two days after administration will be deactivated and the rest of study subjects will receive the predefined higher dose level of the study drug (over 300 µg) without hospitalization. If two or more of the first six evaluable subjects fail to meet the criteria for tolerability, the Coordinating Principal Investigator, the Principal Investigators at each site and the sponsor's Medical Monitor will perform a comprehensive assessment of continuation of the study.

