Study Design: This is a Phase 2 single arm study to investigate efficacy and safety of P1101 for adult Japanese patients with PV. Eligible patients will be treated with P1101, starting at 100 $\mu$ g (or 50 $\mu$ g in patients under another cytoreductive therapy). The dose should be gradually increased by 50 $\mu$ g every two weeks (in parallel, other cytoreductive therapy should be decreased gradually, as appropriate) until stabilization of the hematological parameters is achieved (hematocrit <45%, platelets <400 $\times 10^9/L$ and leukocytes <10 $\times 10^9/L$ ). The maximum recommended single dose is 500 $\mu$ g injected every two weeks.  At week 36 (month 9) and week 52 (month 12), the primary study endpoint, phlebotomy-free CHR, will be analyzed. After completion of the 52-week study duration, provision and administration of P1101, collection of the long-term follow up information (blood parameters, molecular and	

cytogenetic data, safety parameters and as also the optional bone marrow data) will be continued until the drug becomes commercially available for all study subjects..

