### **Study Procedures:**

For eligibility purposes, local lab data and local evaluations (incl. mutational status, bone marrow) will be accepted if properly documented in the source data.

Patient visits will be scheduled every 2 weeks: at regular visits, safety and AE data collection with

the basic lab investigations will be performed, while every three months (month 3, 6, 9 and 12) extended assessment visits will be scheduled. A safety follow-up visit will take place 28 days after the end of the last treatment visit.

Study procedures are detailed in the study flowchart (Appendix 1).

Pharmacokinetic (PK) samples will be collected once every 2 weeks at a timing prior to drug administration (at steady state), four consecutively at Week 0 (at first dose) and Week 28 (Appendix 2), at the end of treatment visit, and at the safety follow-up visit.

Assessment of safety will be determined by vital sign measurements, clinical laboratory tests, physical examinations, spleen size measurement by ultrasound, electrocardiogram (ECG) evaluation, lung X-ray, Eastern Cooperative Oncology Group (ECOG) performance status, ophthalmologic investigations, and the incidence and severity of treatment-emergent AEs (TEAEs).

At screening, month 9 and 12, central lab will be testing Hct, WBC and platelets for the purposes of primary endpoint analysis.

Also, a central lab will be in charge of the quantitative allelic burden measurement, as also will perform all further evaluations.

Local labs will be used for other measurement in the study.

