# 7 STUDY ENDPOINTS

## 7.1 Primary Efficacy Endpoint

The primary efficacy endpoint is the phlebotomy-free complete hematologic responder rate (CHR) at month 9 and month 12.

The phlebotomy-free responder rate is defined as the proportion of patients with complete hematologic response (CHR) and with no phlebotomies during the previous 3 months.

A responder in sense of a primary endpoint is a patient who has met all of the following criteria at month 9 and month 12:

- Hematocrit <45% phlebotomy-free (absence of phlebotomy during the previous 3 months)
- Platelet count  $\leq 400 \times 10^9/L$ ,

- 
- WBC count  $\leq 10 \times 10^9/L$

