## **24 APPENDICES**

## 24.1 Appendix 1. Study Flowchart

	Screening	Treatment phase		End of Treatment	End of Study (Safety follow-up visit)
		every 2 weeks, except visits co-incident to the Assessment visits		Assessment visits - every 12 weeks (month 3, 6 and 9)	Month 12 / Premature discontinuation visit
Informed consent	X				
Inclusion and exclusion criteria	X				
Demographics & medical history	X				
Pregnancy test (urine)	X	X (Every 4 weeks from Week 0)	X	X	X
Heart ECHO standard	X			X	X (cases with early termination only)
12-lead ECG	X	Week 0, Week 0 +96 h Week 2, Week 4, Week 28, Week 28 + 96 h	X	X	X
Physical examination	X	X	X	X	X

Vital signs	X	X	X	X	X
Blood chemistry small panel	X	X	X	X	X
Blood chemistry large panel	X		X	X	
Coagulation (blood)	X		X	X	X
Virology (blood)	X				
Hemoglobin A1c HbA1c)	X				
Hematology small panel	X	X	X	X	X
Hematology large panel	X		X	X	
Immunological parameters (blood)	X		X	X	X
Urine test	X	X	X	X	X
Urine beta 2 microglobulin test	X			X	
ECOG performance status	X	Week 0 only	X	X	X
Spleen size measurement	X	Week 0 only	X	X	
Genetic and mutation test sample (incl. JAK2 allelic burden) (blood)	X	Week 0 only	X	X	
Bone marrow sampling (OPTIONAL)	X			X	
P1101 administration		X	X		
Adverse events	X	X	X	X	X

Concomitant treatment	X	X	X	X	X
Immunogenicity (blood)		Week 0 and Week 4 (Week 0: 0 hr. and 168 hr.) (Week 4: 0 hr.) see Appendix 3	X	X	X
PK (blood)		X (Trough value at every dosing) (4 sampling points per visit at Week 0 and Week 28, see Appendix 2)	X	X	X
HADS	X		X	X	X
Ocular examination	X			X	
Lung X-ray	X			X	

---

Vital signs:	Pulse rate, blood pressure and body temperature.
Blood chemistry small panel:	BUN, ALT, AST, GGT, LDH, total bilirubin.
Blood chemistry large panel:	NT-proBNP or BNP, $\text{Na}^+$ , $\text{K}^+$ , $\text{Ca}^{++}$ , $\text{Cl}^-$ , uric acid, blood glucose, alkaline phosphatase, amylase, lipase, creatinine, total protein, albumin, LDL, HDL, cholesterol, triglycerides, serum iron, transferrin, TSH and fT4.
Coagulation (Blood):	PT-INR, aPTT and fibrinogen.
Virology:	Serology: HBsAg, HCV antibody, HIV antibody
Hematology small panel:	Hemoglobin, hematocrit, platelet count, RBC, WBC.
Hematology large panel:	WBC differential (neutrophils, lymphocytes, monocytes, eosinophils, basophils and reticulocytes), MCV
Immunological parameters:	ANA, TgAb (autoantibodies to thyroglobulin), TPOAb (autoantibodies to thyroid peroxidase).
Urinalysis:	pH, blood, protein, glucose, WBC, nitrite

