4.3.4.2 Secondary Variables

- Changes in HCT, WBC, PLT and Spleen Size from baseline
 - Absolute values and changes will be computed over study timepoint (Months 3, 6, 9 and 12)
- Time to first phlebotomy
 - Time to first phlebotomy is defined as the time interval from first dosing to first time when subject experiences a phlebotomy procedure. Subjects who completed the study and never had a phlebotomy procedure will be censored at the end of the study (Month 12). Subjects who discontinued from the study prior to any phlebotomy procedure will be censored at the time of discontinuation.
- Numbers of phlebotomy
 - Number of phlebotomy procedures experienced will be categorized as 0, 1, 2, 3 and >3.
- Disease response over time (DRT)
 - DRT will be derived from hematology parameters (Hematocrit <45% without phlebotomy (at least 3 months since last phlebotomy), and platelets $\leq 400 \times 10^9/L$, and WBCs $\leq 10 \times 10^9/L$). Central laboratory assessments will be used for disease response assessment at Weeks 12, 24, 36, 52. Patients, who withdraw early for any reason, will be classified as treatment failures in visits that they did not complete. Disease response based on local laboratory assessment will be analyzed as a sensitivity analysis if the data is available.

Protocol P1101 in Japanese PV (A19-201)

- Time to first peripheral blood count response

Time to first peripheral blood count response is defined as the time interval from first dosing to first time when achieving disease response (Hematocrit <45% without phlebotomy (at least 3 months since last phlebotomy), and platelets $\leq 400 \times 10^9/L$, and WBCs $\leq 10 \times 10^9/L$). Subjects who completed the study and never achieved response will be censored at the end of the treatment (Month 12). Subjects who discontinued prior to achieving a disease response will be censored at the time of discontinuation.

- Duration of peripheral blood count response maintenance:

Duration of response maintenance will be calculated as number of days starting from assessment visit when the response was achieved till date (excluding) of assessment visit when the response was lost. If more response period occurred within one patient, the longest period will be used for analysis. Number of days will be divided by 30.5 and results presented in months. Only subjects with response will have the duration.

- Change from baseline of *JAK2* allelic burden over time

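### Section 12.1 stops dose escalation on a different trigger from the synopsis and SAP 2.1, and read literally its response trigger cannot act before 500 µg is due

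*Protocol*

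**What the plan says.** Two stop rules for escalation stand in the current text.

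- **Synopsis (Study Design; Investigational Product) and SAP 2.1.** The dose goes up by 50 µg every two weeks "until stabilization of the hematological parameters is achieved", with hematocrit <45%, platelets <400 x 10^9/L and leukocytes <10 x 10^9/L, and a maximum of 500 µg. No phlebotomy-free interval and no visit are named. The synopsis adds that the dose is then kept at the highest tolerated level that gives the best response.
- **Protocol 12.1.** The dose goes up to 500 µg, "or until response (as defined by primary endpoint) will be achieved". Then: "The dose then will remain fixed for the study duration". A step back to the prior dose is allowed for safety or tolerability.

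Protocol 7.1 defines the primary-endpoint responder as "a patient who has met all of the following criteria at month 9 and month 12", with no phlebotomy in the previous 3 months. Protocol 12.5 speaks only of response, without saying which. For patients on hydroxyurea (HU), 12.1 refers to Appendix 7. That starts P1101 at 50 µg and adds 50 µg every two weeks through Week 12, with no count-based stop, while HU is withdrawn.

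SAP 4.3.4.2 also has a visit-level response: "Hematocrit <45% without phlebotomy (at least 3 months since last phlebotomy"), plus the platelet and WBC limits, at Weeks 12, 24, 36 and 52.

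**The concern.** A patient who tolerates the drug and whose counts are in range is held under the synopsis and SAP 2.1, but goes on escalating under 12.1 as written. Sites working from different sections could therefore dose similar patients differently.

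This matters most above 300 µg. Protocol 12.1 itself cites a lack of Japanese experience there, and requires two-day admission at 350 to 500 µg until the 500 µg review is passed. Once a patient has been escalated past control, nothing lowers the dose because the counts are controlled: Protocol 12.5.2 ties reduction to safety and tolerability alone. Exposure, and any safety or exposure-response reading from about 30 patients, would depend in part on which sentence a site followed.

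**Working it through.** **Inputs.** Start 100 µg at Week 0, plus 50 µg every 2 weeks, cap 500 µg (Protocol 12.5). Start 50 µg for patients on HU (Appendix 7). Endpoint visits are Weeks 36 and 52 (synopsis). The limit for reaching 500 µg is 32 weeks (Protocol 12.1). Dosing is every 2 weeks from Week 0 to Week 50, which is 26 doses. No delays or toxicity holds are assumed, and local results are taken as known before dosing.

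**Step 1: reproduce the schedule.** Dose at week w = min(500, start + 25w).

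| Week | 100 µg start | 50 µg start (HU) |
|---|---|---|
| 0 | 100 | 50 |
| 2 | 150 | 100 |
| 4 | 200 | 150 |
| 10 | 350 | 300 |
| 12 | 400 | 350 |
| 16 | 500 | 450 |
| 18 | 500 | 500 |

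The first three values at 100 µg match the 100, 150 and 200 µg stated in Protocol 12.5.

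**Step 2: literal 12.1.** Response at both visits is known at Week 52, which is 52 - 16 = 36 weeks (HU: 52 - 18 = 34) after 500 µg is due. If one visit were enough, as one sentence of SAP 2.3.1.1 allows, it would be Week 36: 20 weeks (HU: 18) after 500 µg is due, and 4 weeks after the 32-week limit. The 500 µg branch always acts first.

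**Step 3: visit-by-visit reading.** Take 3 months as 12 weeks, so a patient phlebotomised at Week p cannot qualify before Week p + 12. Protocol 14.1 calls for phlebotomy whenever hematocrit is 45% or higher. From a 100 µg start:

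- p = 0: earliest Week 12; 350 µg already given, 400 µg due.
- p = 4: earliest Week 16; 450 µg already given, 500 µg due.
- p = 6: earliest Week 18; 500 µg already given at Week 16.

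With no phlebotomy in the previous 3 months, that condition is met at once. If 2-weekly counts are used, the two rules then largely coincide. If response is read only at the quarterly visits ("Assessment visits - every 12 weeks (month 3, 6 and 9")), the first opportunity is Week 12 for everyone, with 400 µg due (350 µg on HU).

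**Step 4: size for one illustrative patient.**

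- 100 µg start, literal 12.1: 100 + 150 + ... + 500 = 2,700 over 9 doses, plus 17 x 500 = 8,500; total 11,200 µg.
- 100 µg start, held at the Week 4 dose: 100 + 150 + 24 x 200 = 5,050 µg. Ratio 11,200 / 5,050 = 2.2.
- HU, literal 12.1: 50 + 100 + ... + 500 = 2,750 over 10 doses, plus 16 x 500 = 8,000; total 10,750 µg.
- HU, Appendix 7 followed to 300 µg at Week 10, then held: 50 + 100 + ... + 300 = 1,050 over 6 doses, plus 20 x 300 = 6,000; total 7,050 µg. Ratio 10,750 / 7,050 = about 1.5.

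**The case against.** The best defence is that nobody writes a stop that can never act, so response in 12.1 must mean the component criteria at a visit. There is support for this. Protocol 17.4.1 assesses response at each 3-month time point, SAP 4.3.4.2 defines it by visit, and Appendix 7 speaks of a dose allowing CHR from Week 13. This stands as a plausible intent, and it narrows the problem. It does not remove it, because the 3-month phlebotomy condition remains in 12.1 and is absent from the synopsis and SAP 2.1.

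The synopsis sentence on the highest tolerated dose also means that the synopsis is not a bare hold-when-in-range rule. But that sentence concerns maintenance, and it leaves the stabilisation stop in the same paragraph in place. The figure after the 12.1 dosing text is not shown in the copy reviewed. It may clarify the scheme, but the written rules still differ. The SAP says that it follows protocol version 3.0; that does not explain the conflict, since the synopsis of version 4.0 carries the same wording as SAP 2.1.

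A reader might infer more than the documents support:

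- **That an HU patient would be held at 150 µg from Week 4.** Appendix 7 sets escalation through Week 12 without a count-based stop, so the comparison starts from 300 µg.
- **That excess dose is never corrected.** Protocol 12.5.2 interrupts or reduces for toxicity and neutrophil falls, 12.5 only prefers a fixed dose, and 12.1 requires review before each step above 300 µg. What is missing is a reduction because counts are controlled.
- **That doses above 300 µg are themselves a fault.** They are planned. Protocol 5.6 reports 40.18% of subjects at a 500 µg plateau and 60.53% at 350 µg or higher in the earlier programme.

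**Conclusion.** The point holds as a conflict between current dosing texts. Taken literally, 12.1's response stop is inoperable on the planned schedule. On the more generous reading it still differs from the synopsis and SAP 2.1 for patients phlebotomised on study.

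The dose totals are illustrations. They assume an uninterrupted schedule, and the lower totals assume counts controlled from Week 4 (100 µg start) or at Week 10 (HU). They are not estimates of average excess exposure. The number of patients affected cannot be derived, because the plateau percentages do not separate stopping for response from stopping for tolerability.

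A reader might also infer that the efficacy test is compromised. The documents do not support that: the stated power rests on CHR rates of 11% and 36% with 25 cases, and dose does not enter it. The sponsor should correct this, but it does not call the sample size or the primary analysis into question.

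**What to change.** In Protocol 12.1, replace the reference to primary-endpoint response with the rule of the synopsis and SAP 2.1: escalate "until stabilization of the hematological parameters is achieved", with hematocrit <45%, platelets <400 x 10^9/L and WBC <10 x 10^9/L, read at each 2-weekly visit on local counts. Also:

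- State whether a phlebotomy-free interval is required for dosing and, if so, how long.
- State that Appendix 7 governs patients on active HU until HU is stopped.
- Reconcile the fixed dose in 12.1 with the synopsis sentence on the highest tolerated dose giving the best response.
- Use the same wording in the synopsis, Protocol 12.5 and SAP 2.1.

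Whether to require confirmation at a second visit, or to resume escalation when counts are lost, is a clinical choice for the sponsor and is not part of the required change.

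**Cost.** A protocol amendment with IRB approval (Protocol 21.1), matching SAP text and a site letter. No added visits or samples: the 2-weekly small panel already covers "Hemoglobin, hematocrit, platelet count, RBC, WBC", and apart from the central tests the synopsis says "Local labs will be used for other measurement in the study".

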## 12.2 Physical, Chemical, Pharmaceutical Properties, and Formulations

The chemical name of P1101 is poly(oxy-1,2-ethanediyl),  $\alpha$ -hydro- $\omega$ -methoxy-,1,1-diester with interferon  $\alpha$ -2b [1-[1-[3,7-bis(carboxyamino) heptyl] proline].

P1101 is available as a solution containing P1101, sodium chloride, polysorbate 80, benzyl alcohol, sodium acetate anhydrous, acetic acid, sodium hydroxide, hydrochloride acid, and water for injection. The solution is colorless to light yellow. P1101 will be supplied in pre-filled syringes.

The structural formula and amino acid sequence for P1101 is provided in Figure 12-1.

**Figure 12-1 P1101 Structural Formula and Amino Acid Sequence**

Due to innovative pegylation technology, P1101 is composed of a single isoform. Recombinant IFNs as well as pegylated recombinant IFNs have been approved in several countries in various indications based on their antiviral, antiproliferative, and immunoregulatory properties.

### 12.3 Packaging, Labeling and Storage

The study drug will be labelled in the local language and comply with the legal requirements of each country. The study drug will include the following labeling: “For Clinical Trial Use Only,” “To be administered at a dose according to the physician’s instructions,” and “Keep out of reach of children.” The labels will include storage conditions for the study drug and the study drug number, but no information about the subject.

Additionally, aspirin (aspirin) 75 to 150 mg per day as background therapy (provided locally) will be prescribed to all subjects (unless contraindicated). In this case, other prophylactic antithrombotic agents may be used.

**Table 12-1 Packaging and Labeling**

Study drugs	Packaging
P1101	Pre-filled syringes with 500 µg per syringe

P1101 pre-filled syringes will be shipped in cooled containers. Pre-filled syringes must be refrigerated immediately upon receipt to ensure optimal retention of physical and biochemical integrity and should remain refrigerated until just prior to use. Study drug should be stored by the study site at controlled room temperature of 2 to 8°C. Temperature logs must be maintained to ensure proper storage conditions. Do not freeze or shake the pre-filled syringes. Do not use medication beyond the expiration date stamped on the PFS. PFS must be kept in their outer carton to protect them from the light.

If the temperature of study drug storage in the clinic/pharmacy exceeds or falls below the 2°C to 8°C range, this should be reported to the Sponsor/designee and captured as a temperature excursion. Additional details on study drug storage requirements and related information will be provided in the pharmacy manual.

### 12.4 Supply of Study Drug at Site

The Sponsor/designee will ship the study drug to the investigational sites. The initial study drug shipment will be authorized by the Sponsor/designee after all required regulatory documentation for a particular site has been received. Subsequent study drug shipments will be made after site request for resupply. Details will be included in the pharmacy manual.

The study drug must be received by the study pharmacist or designated person at the study site, handled and stored safely and properly, and kept in a secured location to which only the study pharmacist and designated assistants have access. Upon receipt, the study drug should be stored according to the instructions specified on the drug labels. All drug product must be accounted for in accordance with the standard practice at each study center and in compliance with applicable regulations. The site must use an appropriate dispensing log/accountability form provided by the sponsor, or an acceptable substitute approved by the sponsor. Each time study medication is dispensed for a subject, the following information must be recorded: the subject’s unique identifying number, the dose strength, the number of units (syringe) with the corresponding lot number, and the initials of the person dispensing the drug. These logs are to be maintained by the study pharmacist in the pharmacy throughout the duration of the study and will be periodically verified by a representative of the sponsor.

